#### A3a. Financial Conflict of Interest

Does any member of study personnel (Investigator (including investigator's spouse and/or dependent children)) that are involved in the design, conduct, or reporting of the research have a Significant Financial Interest (SFI) that would reasonably appear to be affected by the research for which funding is sought and/or associated with an entity/business that would reasonably appear to be affected by the research?

No

#### A5. Funding Source:

Organization: GILLSON LONGENBAUGH FOUNDATION

#### A6a. Institution(s) where work will be performed:

BCM: Baylor College of Medicine

#### A6b. Research conducted outside of the United States:

Country:  
 Facility/Institution:  
 Contact/Investigator:  
 Phone Number:

If documentation of assurances has not been sent to the Office of Research, please explain:

#### A7. Research Category:

#### A8. Therapeutic Intent

Does this trial have therapeutic intent?

Yes

#### A9. ClinicalTrials.gov Registration

Does this protocol/trial require registration on ClinicalTrials.gov due to it: meeting the definition of an Applicable Clinical Trial, being required under the terms and conditions of an award, or being proposed to be published in ICMJE journals?

Yes

Who will be responsible for registering and maintaining the registration of this Applicable Clinical Trial?

The BCM PI will register the trial because either:

- the trial is BCM PI-initiated,
- BCM is the lead site of this multicenter trial, or,
- the industry sponsor has instructed the BCM PI to register the trial, or,
- registration of this trial is required as a term and condition of the reward by the funding agency.

ClinicalTrials.gov Identifier:

NCT

### Section B: Exempt Request

#### B. Exempt From IRB Review

Not Applicable

### Section C: Background Information

Anxiety and obsessive-compulsive disorders are the most common mental health disorders in childhood and adolescence (Merikangas et al., 2010). Parental accommodation of their children's avoidance, escape, safety behaviors are a set of parenting behaviors that have been most strongly associated with child anxiety and obsessive-compulsive disorder (Kagan et al., 2016). Developing and testing parent-led interventions that target accommodation and parenting styles associated with anxiety has the potential to improve treatment outcomes and reach families who may not otherwise access care (for

example, for youth who refuse to attend therapy). A parenting intervention for youth with anxiety has been recently developed to address these goals called Supportive Parenting of Anxious Childhood Emotions ("SPACE"). In this intervention, therapists meet individually with parents to help them reduce accommodation and support adaptive behaviors in their children. SPACE was recently shown to be noninferior to individual cognitive-behavioral therapy with 88% of youth being classified as responders to SPACE (Lebowitz et al., 2020).

The purpose for the proposed study is to demonstrate the treatment efficacy of SPACE compared to a low-contact, therapist-supported bibliotherapy version of this intervention, providing efficacy evidence for SPACE as delivered by an independent investigatory group.

## Section D: Purpose and Objectives

The purpose of this study is to implement a parenting intervention based on a cognitive-behavioral approach to anxiety and OCD for children and adolescents aged 7-17. We will compare standard Supportive Parenting for Anxious Childhood Emotions (SPACE) to a low-contact, therapist-supported bibliotherapy version of SPACE using the book "Breaking Free of Child Anxiety and OCD."

Specifically, our aims are as follows:

1. To provide evidence of treatment efficacy for the full standard version of SPACE relative to a low therapist contact bibliotherapy version of SPACE (Lebowitz, 2020).
2. To determine pre-treatment predictors of treatment outcome, especially those that showed a moderate response to the low therapist contact bibliotherapy SPACE group compared to the standard SPACE group.
3. To compare treatment adherence between the standard SPACE group and the low therapist contact bibliotherapy SPACE group.
4. To explore treatment satisfaction, preferences, and feasibility of standard SPACE and low therapist contact bibliotherapy SPACE, overall and as a function of group status.

## Section E: Protocol Risks/Subjects

### E1. Risk Category

Category 2: Research involving greater than minimal risk, but presenting the prospect of direct benefit to the individual subjects.

### E2. Subjects

Gender:

Both

Age:

Adolescent (13-17 yrs), Adult (18-64 yrs), Child (3-12 yrs), Geriatric (65+ yrs)

Ethnicity:

All Ethnicities

Primary Language:

English

Groups to be recruited will include:

Both patients and healthy, non-patient, normals

Which if any of the following vulnerable populations will be recruited as subjects?

Children, Mentally ill

Vulnerable populations require special protections. How will you obtain informed consent, protect subject confidentiality, and prevent undue coercion?

There are two types of participants in this study. First, parents of children anxiety and/or OCD will provide informed consent, and only those adults with decisional capacity will be eligible for participation. These participants (i.e., parents) are not considered a vulnerable population. Second, children with anxiety and/or OCD are considered a vulnerable population. Therefore, their parents are required to provide consent and the child will be asked to provide assent. Information provided to children will be suitable for their developmental level. Further, we have exclusion criteria related to low IQ to ensure children are able to understand the purpose and nature of the study.

Overall, all participants will be provided with all relevant information and will be given as much time as needed to decide whether to participate. Participants will be informed that their participation or absence of participation will not have any influence on the clinical services received at BCM or any other institution. Informed consent/assent will be obtained prior to proceeding with any study procedures. We will take all appropriate steps to protect participants' identities. Participants will be assigned a unique alphanumeric identifier that will enable the research team to manage the participant data while maintaining the participant's confidentiality. All study data will also be coded with the participants' unique identifier. The coded data will be stored on servers managed by the institutional IT programs and/or departmental system administrators. Any physical data will be examined in a secure and private environment. When not in use, the physical data will be locked in a filing cabinet located in the research team's office, where only the research team has access. We will collect the minimum amount of information needed for the purposes of this study. Only approved study personnel will have access to this data, and all of the information gathered will be used for this study, only unless data has clinical relevance to the patient's treatment, in which case will be shared with the clinical team.

### **E3. Pregnant woman/fetus**

Will pregnant women and/or fetuses (as described in 45 CFR 46 Subpart B) be enrolled in the research?

No

### **E4. Neonates**

Will neonates of uncertain viability or nonviable neonates (as described in 45 CFR 46 Subpart B) be enrolled in the research?

No

### **E5. Children**

Will children be enrolled in the research?

Yes

## **Section F: Design/Procedure**

### **F1. Design**

Select one category that most adequately describes your research:

c) Pilot

Discuss the research design including but not limited to such issues as: probability of group assignment, potential for subject to be randomized to placebo group, use of control subjects, etc.

A total of 120 children-parent dyads will participate and will be randomized in a 1:1 ratio into one of two groups: (1) the standard SPACE group and 2) the bibliotherapy, low therapist contact SPACE group.

Inclusion Criteria:

- 1) The child is between the ages of 7 to 17 at enrollment
- 2) The child has clinically significant symptoms of anxiety and/or OCD, as indicated by a score of 12 or higher on the Pediatric Anxiety Rating Scale (PARS).
- 3) The child is appropriate for anxiety-focused treatment (e.g., anxiety is the primary problem as diagnosed using the Kiddie Schedule for Affective Disorder and Schizophrenia (K-SADS), and if secondary psychopathology is present it will not interfere with treatment).
- 4) One parent/guardian is able and willing to participate in assessment and treatment (e.g., has sufficient English fluency, the decisional capacity to participate, and can commit to treatment duration).
- 5) The participating parent/guardian lives with their child at least 50% of the time.
- 6) Both parent and child are able to read and understand English.
- 7) The child has the intellectual and communication skills to engage in CBT, as judged by an experienced supervising clinician.
- 8) Participants must reside in Texas and parents must be in the state of Texas when taking calls.

Exclusion Criteria:

- 1) the child has a diagnosis of child lifetime bipolar disorder, drug or alcohol abuse, psychotic disorder, or conduct disorder.
- 2) the child has severe, current suicidal/homicidal ideation and/or self-injury requiring medical intervention (referrals will be made for appropriate clinical intervention).
- 3) the child is receiving concurrent evidence-based psychotherapy for anxiety, involving exposure therapy in at least 50%

of sessions.

4) New Treatments: Initiation of an antidepressant within 12 weeks before study enrollment OR 6 weeks for an antipsychotic, benzodiazepine, or ADHD medication before study enrollment. Established Treatment changes: Any change in established psychotropic medication (e.g., antidepressants, anxiolytics, alpha agonist) within 6 weeks before study enrollment (4 weeks for antipsychotic, anti-anxiety, benzodiazepine, or ADHD medication). Any medications must remain stable during treatment; downward adjustments due to side effects may be acceptable.

## F2. Procedure

**RECRUITMENT.** A total of 120 child-parent dyads will be recruited through different methods. The primary sources will be through the Baylor Psychiatry Clinic, social media, and various anxiety and OCD-related organizations, professionals, clinics, and resources.

Study advertisements will be circulated through other relevant sources (e.g., social media, including Facebook ads and videos of the PI talking about the study; websites; listservs; newsletters; research participant databases; word of mouth; other sources that would provide a diverse sample to enhance enrollment and subject generality).

We will contact social service/community organizations (e.g., private clinics, educational support/other social emotional learning services, schools, advocacy groups, resources, nonprofits) to distribute flyers.

Standard disclaimer language from the organization distributing the study flyer may be included on the flyer (these disclaimers state that the flyer content isn't coming from the organization; see example in Section S).

Interested people will be asked to contact the coordinator by email/phone.

**PHONE SCREEN.** Parents will be given a 20-minute telephone screening to elicit preliminary inclusion/exclusion information, confirm potential interest, and answer questions the parent may have about the study. A screening form will be used to collect pertinent information including contact information, basic demographics (age, race, gender, ethnicity), and questions relating to mood and health. Individuals who meet basic eligibility requirements during the phone interview and remain interested will be invited for a screening visit (i.e., baseline assessment), at which point a member of the research team will obtain informed consent/assent from the parent and child.

**INFORMED CONSENT.** There are three possibilities for obtaining consent if and when a potential participant chooses to participate in this study.

1) Consent will be obtained in-person. Participants will be provided with all relevant information and will be given as much time as needed to decide whether to participate. The person obtaining consent will thoroughly explain each element of the document and outline the risks and benefits, alternate treatment(s), and requirements of the study. The consent process will take place in a quiet and private room, and participants may take as much time as needed to make a decision about their participation. Members of the research team will be available to answer questions or explain any details further. Participants will be informed that their participation or absence of participation will not have any influence on the clinical services received at BCM (or any other institution). Informed consent/assent will be obtained prior to proceeding with any study procedures. A copy of the informed consent form will be given to the subject to take home with them. All participants will also be informed that they do not have to answer any specific questions if they do not wish to do so.

2) Consent will be obtained using an electronic process. All regulatory consent procedures explained above will be followed when using e-consent protocol i.e. provided all relevant information and be given as much time as needed. A member of the research team will schedule an informed consent via HIPAA compliant video conferencing software, ZOOM. Participants will be provided an electronic copy of the consent to read prior to the call. Research staff will send the participant a secure e-mail link to an online consent form via Redcap. We will also provide 'key points' to the study, to aid in the parents explanation of the study to their child so that the child has an understanding of the study, requirements, and components prior to the scheduled call. During the scheduled call, participant and research team member(s) will thoroughly review the consent to ensure comprehension, answer any questions, and address any concerns. Participants will be able to agree to participate, and sign the consent form with a stylus, mouse, or finger and submit it to the research staff. The participant will also be able to download a copy of their signed consent form as a PDF through REDCap.

3) Consent will be obtained via mail. Alternatively, participants have the option of receiving the informed consent in hard-copy via mail. The research team will mail 2 consent forms to the participant. The consent discussion will be conducted over the phone before the participant signs the forms. Members of the research team will be available to answer questions or explain any details further. The participant will be instructed to sign both, keep one for their records, and mail back the second using the self-addressed stamped envelope included in the mailing. Informed consent will be obtained prior to proceeding with any study procedures.

**TREATMENT.** All participants will receive the Supportive Parenting of Anxious Childhood Emotions (SPACE) intervention, a parenting intervention based on a cognitive-behavioral approach to anxiety. In SPACE, parents learn to support their children through instilling a message of support and encouragement; that they acknowledge their child's difficult experience with anxiety while conveying confidence that they can cope with stressful situations. This is done through specifically identifying parental accommodation behaviors they currently use and steadily reducing engagement in those behaviors. In the therapist-led SPACE group, therapists will follow the SPACE treatment manual, "Treating Childhood and

Adolescent Anxiety." In the low therapist contact bibliotherapy SPACE group, treatment will be provided using "Breaking Free of Child Anxiety and OCD," which is a parent-oriented book adaptation of the SPACE program for child and adolescent anxiety and/or OCD.

Treatment will take place over 12-24 weeks through telemedicine technology (video-conferencing) which, given recent changes in Texas legislation, provides a sustainable platform for disseminating services to those in underserved areas. Treatment begins with psychoeducation about childhood anxiety and how parenting behaviors can contribute to the development and maintenance of anxiety. Subsequently, each week, parents learn tools to increase supportive communication that conveys a message of support (i.e., that they understand and accept their child's distress) and encouragement (i.e., that they are confident in their children's ability to cope). One core aspect of treatment will be parents identifying and steadily reducing specific accommodation behaviors. For example, parents who routinely speak for their child at family gatherings due to their child's social anxiety may tell their child they do not plan on answering questions directed to their child from specific family members, and subsequently resist providing answers when their child is asked questions. Alternatively, parents of children with separation anxiety who usually accompany them on trips outside the house may go on incrementally longer errands while the child is safe at home. These exercises serve as parent-led exposures, the key component of therapy for anxiety.

All relevant information regarding parent-led exercises will be detailed in the treatment manuals/parent-directed books. Therapists will review progress with parents during video-conferencing sessions.

Families will be randomized in a 1:1 ratio into either the low therapist contact bibliotherapy SPACE group or the standard SPACE group. Treatment will be guided by a licensed psychologist/therapist or trainee under the supervision of a licensed psychologist. All treatment will be provided via Zoom, which is HIPAA compliant and secure video-conferencing software.

In addition to posttreatment assessments at the end of the 12-week protocol, a one-month follow-up will assess the sustainability of improvement over a short period. Participants in the low therapist contact bibliotherapy SPACE group who do not reach treatment responder status as assessed at the one-month follow-up will be invited to receive up to additional 8 additional weekly sessions of standard SPACE treatment.

**LOW THERAPIST CONTACT BIBLIOTHERAPY SPACE GROUP (LTC-SPACE group).** Families randomized to the LTC-SPACE group will receive four 45-minute supportive video calls with a therapist over the first 12 weeks of treatment. Participating families will receive a copy of the book 'Breaking Free of Child Anxiety and OCD' to use at home and in-session with the therapist. During each of the four video-conferencing sessions, therapists will serve to provide encouragement and support as the parent works through the program independently, consistent with previous bibliotherapy research (Rapee et al., 2008) and our ongoing work with parent-led bibliotherapy interventions. Treatment-responder status will be determined based on the 1-month follow up assessment (described below), and treatment non-responders will be offered the chance to receive up to eight additional sessions of standard SPACE treatment. Treatment responders will not receive this additional treatment.

**STANDARD SPACE GROUP.** Families randomized to the standard SPACE group will receive twelve parent-only, once-weekly, 60-minute video calls with a therapist. During each of the twelve videoconferencing sessions, therapists will guide the parent through the implementation of the program, including providing psychoeducation, discussing and practicing supportive communication, identifying accommodation behaviors, and developing weekly goals related to reducing accommodation. Participants in this group will not be offered an additional 8-week course of standard SPACE regardless of treatment-responder status determined at the 1-month follow up assessment.

**ASSESSMENTS.** All participants will be asked to cooperate in assessments that will occur at pre-treatment (baseline before treatment), post-treatment (at the end of the twelve weeks), and 1-month follow up (4 weeks after first 12 weeks of treatment have concluded). Non-responders to bibliotherapy (assessed at 1-month follow-up) who choose to participate in therapist-led SPACE will complete an additional post-treatment assessment following up to eight additional sessions of SPACE (up to 8 weeks later). The three assessments include a battery of questionnaires and measures at these three timepoints. Depending on group assignment (LTC-SPACE or standard SPACE), measures will also be completed at session visits. Treatment responder status will be assessed at the 1-month follow up, and whether participants in the LTC-SPACE group receive up to 8 additional weeks of standard SPACE will be determined based on the 1-month follow up assessment.

The IE will be an experienced clinician, trained professional, or advanced graduate trainee (supervised by a clinician). The measures that will be administered will include both IE-rated and participant-rated scales (please see attachment in section S). Measures will be completed either in-person or by secure connection (Zoom) and Qualtrics, to reduce burden.

**TREATMENT FIDELITY/INTEGRITY.** All clinician and assessment sessions, in both conditions, will be audio-recorded or video-recorded (with parent consent). These recordings will be used for research purposes, to monitor ongoing fidelity, to quantify treatment adherence, as well as to assess inter-rater reliability and rater drift. If concerns are noted, the clinician and/or IE will not conduct another assessment until procedures have been reviewed. Clinicians will upload audio and video recordings to a web-secure, HIPAA-compliant storage (Box). Fidelity measures have been developed in our pilot work and adapted for use in this project: [1] The Parent Completion and Effort Rating (PCER); and [2] The Treatment Adherence, Content, and Competence Checklist. We will also use treatment fidelity checklists for each session following Lebowitz et al. (2020).

## Section G: Sample Size/Data Analysis

### G1. Sample Size

How many subjects (or specimens, or charts) will be used in this study?

Local: 240      Worldwide: 240

Please indicate why you chose the sample size proposed:

We will enroll 120 parent-child dyads (n = 240 total children and parents), we anticipate 90 dyads will be eligible (n = 180), in order to meet an intent-to-treat sample size of 45 parent-child dyads per group, accounting for screen-fail rates. This exceeds our anticipated needs of 34 parent-child dyads per group to detect statistical significance in response rates on the CGI-I, the primary outcome measure. The power analysis assumed  $\alpha = .05$ , power = .95, as well as a 24% response rate for the parent self-guided intervention (based on our previous work with a similar approach; Storch et al., under review) and a 66% response rate for individual SPACE based on the Lebowitz et al. (2020) trial. We also anticipate the target sample size will be more than enough to detect differences in reductions on the Pediatric Anxiety Rating Scale (PARS), our other primary outcome, based on the Lebowitz et al. (2020) trial and our own preliminary analysis (Storch et al., under review). For this outcome, we anticipate needing 16 participants to detect statistically significant differences. This assumes an effect size of  $f = .845$ ,  $\alpha = .05$ , power = .95, and a correlation among repeated measures of  $r = .33$ .

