### G2. Data Analysis

Provide a description of your plan for data analysis. State the types of comparisons you plan (e.g. comparison of means, comparison of proportions, regressions, analysis of variance). Which is the PRIMARY comparison/analysis? How will the analyses proposed relate to the primary purposes of your study?

Descriptive statistics on all randomized participants will be analyzed and if any key variables (e.g. anxiety severity) differ across groups, they will be controlled for in analytic models via inclusion as a covariate. Violations of distributional assumptions will be addressed (e.g. robust sandwich estimators and interval smoothing for continuous variables, and exact logistic regression) in the case of sparingly distributed dichotomous dependent variables.

Study Aims 1-4 address pre-post group differences as a result of treatment, statistical moderation of pre-post treatment effects, and evaluation of additional observed change from post-treatment to 1-month follow up. Chi-square analyses will compare dichotomous outcomes (i.e., treatment response rates). Mixed within-between (time by treatment group) analysis of covariance (ANCOVA) will be used to assess pre-post and post-1-month follow up changes in continuous outcomes (i.e., symptom severity). Within-group change on continuous measures from post-treatment to 1-month follow up will be assessed by dependent t-tests for each treatment group. Between group differences in study dropout will be assessed by logistic regression.

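### Two primary outcomes are each powered at the full .05, and G2 states no success rule, no multiplicity control and no visit for the response test

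*Combined protocol and SAP*

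**What the plan says.** Section D gives the first aim as "To provide evidence of treatment efficacy for the full standard version of SPACE" relative to the low-contact bibliotherapy version.

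G1 derives 34 dyads per group "to detect statistical significance in response rates on the CGI-I, the primary outcome measure", from alpha .05, power .95 and response rates of 24% and 66%. It then turns to "reductions on the Pediatric Anxiety Rating Scale (PARS), our other primary outcome", again with alpha .05 and power .95: "For this outcome, we anticipate needing 16 participants to detect statistically significant differences". The planned intent-to-treat sample is 45 dyads per group.

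The prompt in G2 asks "Which is the PRIMARY comparison/analysis". The reply lists methods without ranking them:
- Response: "Chi-square analyses will compare dichotomous outcomes (i.e., treatment response rates"), with no visit given.
- Continuous outcomes: a mixed time-by-group ANCOVA "will be used to assess pre-post and post-1-month follow up changes in continuous outcomes".
- Framing: "Study Aims 1-4 address pre-post group differences as a result of treatment", followed by moderation and by further change up to the 1-month follow-up.

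F2 (treatment, LTC-SPACE group and assessments) determines responder status at the 1-month follow-up. Its treatment text describes that same visit as a check on whether improvement lasts.

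**The concern.** A trial with two primary outcomes needs a rule that turns two test results into one conclusion. Here each test has the whole .05 and the rule is missing. If CGI-I and PARS disagree, the protocol does not say whether the first aim has been met. Under an either-wins reading the error rate for that aim is above the stated .05.

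The visit adds a smaller gap. G2's framing points to the end of the 12 weeks, whereas the only responder status the protocol describes is fixed four weeks later. A reader cannot tell from G2 which response rate the chi-square test compares, or whether both primaries refer to the same time.

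**Working it through.** **Inputs from G1:** alpha .05 for each outcome; power .95; response 24% and 66%; 34 per group required and 45 per group planned; for PARS, f = .845, repeated-measures correlation r = .33, and 16 participants. **Assumed:** the correlation between the two outcomes, normality of PARS change, and any response rate other than 24% and 66%.

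**1. The plan's own figures.**

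CGI-I, pooled-variance formula, two-sided, no continuity correction:

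n = [1.960·√(2·0.45·0.55) + 1.645·√(0.24·0.76 + 0.66·0.34)]² / 0.42² = (1.379 + 1.049)² / 0.1764 = 33.4, so **34 per group**, as stated. G1 does not state sidedness. Two-sided is inferred from this match, although a one-sided calculation with continuity correction gives 33.

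PARS, between-group repeated-measures F test, 2 groups and 2 measures: λ = f²·N·m/(1 + (m−1)r) = 0.714·16·2/1.33 = 17.2. Power is .970 at N = 16 and .944 at N = 14, so **16 in equal groups**, as stated.

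Both figures use the full .05.

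**2. Family-wise error if either win counts.** With two two-sided .05 tests and bivariate normal statistics, error = 1 − P(|Z1| < 1.96 and |Z2| < 1.96).

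| Correlation | Error |
|---|---|
| 0 | 1 − 0.95² = 9.75% |
| .3 | 9.5% |
| .5 | 9.1% |
| .7 | 8.3% |
| .73 | 8.2% |

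The last row is a ceiling on the correlation. The largest correlation between a normal score and a binary outcome with rate p is φ(z_p)/√(p(1−p)). At p = .24 this is 0.3109/0.4271 = .728, giving 8.2%. At p = .50 (an assumption) it is 0.3989/0.5 = .798, giving 7.8%.

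These are nominal values. The uncorrected chi-square test with 45 per arm and a 24% rate has exact size .054. A simulation of the actual chi-square and t-tests accordingly gave 10.05% with independent outcomes, and 8.45% when response was an exact cut of the same score.

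**3. Family-wise error if both are required.** 0.05² = 0.25% at correlation 0 and 0.9% at .5; it never exceeds 5%.

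**4. When the missing rule would matter.** Exact binomial power for CGI-I, 45 per arm, 24% in the low-contact arm:

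| Standard SPACE response | Power at .05 | Missed at .05 | Power at .025 |
|---|---|---|---|
| 66% (plan) | .985 | 1.5% | .973 |
| 60% (assumed) | .942 | 6% | .904 |
| 50% (assumed) | .739 | 26% | .626 |
| 45% (assumed) | .570 | 43% | .439 |

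PARS power at f = .845 with 90 dyads exceeds .999 at both .05 and .025. In a trial where CGI-I is missed and PARS is significant, the unstated rule decides the conclusion.

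**The case against.** F1 classifies the design as a pilot. At the planned rates both outcomes would probably be significant. No section says that one win suffices, so a both-required reading, with no inflation, is as open as the other. These points lower the weight of the concern but do not remove it: the first aim is an efficacy claim, both tests are powered at .95, and neither rule is written down.

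On timing, the other side is largely right for PARS. G2 puts pre-post differences first and change to 1 month second, and F2 treats the later visit as a check on durability, so pre-post is the natural treatment interval. For response, F2 consistently uses the 1-month follow-up. What remains is that the chi-square sentence names no visit and the two primaries may be tested at different ones.

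Three stronger readings are tempting but not supported:
- A reader might infer that outcome and visit are both free to choose, which would push the error above 9.75%. The texts just cited largely settle the interval for PARS and the timing of responder status, so this goes too far.
- A reader might infer that the offer of extra sessions to low-contact non-responders biases the 1-month rating. Nothing says raters would act on it, F2 provides for checks of inter-rater reliability and rater drift, and no size can be derived.
- A reader might infer that the sample is too small. It is not: CGI-I keeps 97.3% power at .025.

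**Conclusion.** The concern holds as a gap in the decision rule. G1 has two primaries at .05 each, and G2 supplies no primary comparison, no success rule and no multiplicity control. The inflation to about 8.2% to 9.75% is conditional on an either-wins rule, which the protocol neither adopts nor excludes. It rests on a roughly normal PARS change, a 24% response rate, a non-negative correlation and two-sided tests. A floor of 5% would need perfect correlation, which a binary and a normal outcome cannot reach. The protocol should not be described as running at nearly 10% error; it leaves the error rate undetermined.

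The visit point is a clarification. The whole is worth correcting because the repair is cheap, but it does not threaten the sample size or the trial's feasibility, and its practical weight depends on effects being smaller than planned.

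**What to change.** Before outcomes are examined, add a paragraph to G2 along these lines:

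> The two primary comparisons of standard SPACE with LTC-SPACE are CGI-I response at [visit] and change in PARS from baseline to [visit]. They are tested with the Holm procedure at a two-sided family-wise level of .05. Comparisons at the other visit are secondary.

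A fixed sequence (CGI-I, then PARS) or making PARS secondary would also be acceptable.

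The two visits may be the same or different, provided each is named. If week 12 is chosen for response, first confirm that CGI-I and a definition of response exist at that visit. F2 refers to a measures attachment in Section S, which was not available for this review. The rule for offering extra sessions is not changed.

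**Cost.** No added participants or visits.
- Holm: in the worst case CGI-I is tested at .025, and power falls from 98.5% to 97.3% at 24% versus 66%, or from 74% to 63% if standard SPACE response were 50% (an assumption). PARS power stays above 99.9% at the stated effect. Holm guarantees 5%; the lower figure of about 4.9% or less applies only when neither outcome differs.
- Fixed sequence: CGI-I keeps .05, but PARS cannot be claimed when CGI-I fails (1.5% of trials at the planned rates, 26% at 50%).
- PARS secondary: no power loss for CGI-I, but PARS no longer carries the claim.
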